2.5.4.2 At last adequate tumor assessment date otherwise Duration of response (DoR)

DoR applies only to patients whose best overall response was CR or PR. The start date is the date of first documented response (CR or PR) and the end date is the date of event defined as the first documented progression or death due to underlying cancer. In other words, the start date will be determined using the time the response was first determined and not using the time the response was confirmed. If a patient has not had an event, duration is censored at the date of last adequate tumor assessment. DoR will be summarized for the total population and the cohorts separately. Distribution of duration of response will be estimated using the Kaplan-Meier method and the median response duration will be presented along with 95% confidence interval only if there are sufficient numbers of events.

2.6 Analysis of the key secondary objective

No 'key' secondary objective was defined.

2.7 Analysis of secondary efficacy objective(s)

2.7.1 Secondary endpoints

2.7.2 Statistical hypothesis, model, and method of analysis

The following secondary efficacy variables were analyzed in an explorative manner for the full analysis set (FAS): overall response rate (ORR) by Week 24, progression-free survival (PFS) and overall survival (OS).

ORR within Week 24

The ORR within Week 24 was derived from the sequence of overall lesion responses as described for the primary efficacy variable. The ORR by Week 24 was summarized using frequency tables presenting absolute and relative frequencies together with appropriate confidence intervals. Furthermore, the ORR at EOT was analyzed.

Progression-free survival

Progression-free survival (PFS) is the time from date of start of treatment to the date of event defined as the first documented progression or death due to any cause. If a patient had not had an event, progression-free survival was censored at the date of last adequate tumor assessment. Disease progression for primary efficacy endpoint derivation was assessed using the local investigator's tumor assessment (treating center's radiologist). PFS was summarized using the Kaplan-Meier method. Percentiles (25%, median, 75%) of the event time distribution were presented along with their two-sided 95% confidence interval. Additionally, Kaplan-Meier estimates for the proportions of patients progression-free by Week 48 and Week 72 were presented. The Kaplan-Meier curve (with censored patients at number of patients at risk) was displayed graphically.

Overall survival

Overall survival (OS) is defined as the time from date of start of treatment to date of death due to any cause. If a patient was not known to have died, survival was censored at the date of last

contact. OS was summarized using the Kaplan-Meier method as described above. The Kaplan-Meier curve was displayed graphically. Additionally, the proportion of patients alive at 48 and 96 weeks were presented

2.7.3 Handling of missing values/censoring/discontinuations

Same instructions as for primary analysis

2.8 Safety analyses

The analysis of safety objectives was described in section 10.5.2.1. of the study protocol. All listings and tables are presented for the Safety Analysis Set by pretreatment group and total, i.e. cohorts A, B1, B2, B and total:

- postmenopausal women or men without prior treatment for advanced disease (cohort A)
- pre- and perimenopausal women without prior treatment for advanced disease (cohort B1)
- pre-, peri and postmenopausal women with prior treatment for advanced disease (cohort B2)

The overall observation period will be divided into three mutually exclusive segments:

1. pre-treatment period: from day of patient's informed consent to the day before first dose of study treatment
2. on-treatment period plus 30 days: from day of first dose of study medication to 30 days after last dose of study treatment
3. post-treatment period: starting at day 30+1 after last dose of study treatment.

Goserelin and letrozole after end of treatment were not considered as study treatment, see 5.2.1.

As a sensitivity analysis selected analysis tables (see RAP module 7.1) were displayed for a modified SAF population which excludes patients from centers with a relevant inspection finding.

2.8.1 Adverse events (AEs)

Summary tables for adverse events (AEs) include only AEs that started or worsened during the on-treatment period plus 30 days, the **treatment-emergent** AEs. However, all safety data (including those from the pre and post-treatment periods) will be listed in CSR section 16.2. Absolute and relative frequencies for patients with AEs collected during the pre-treatment and post-treatment period are presented.

The following analyses are presented for the different types of AEs:

	Incidence (frequency table)	Two-level frequency table SOC x PT (MedDRA)	Patient data Listing (section 14.3.1)	Maximum severity (frequency table)	Time to event	Dur- ation of event	Recurrence/ frequency of events per patient
Treatment emergent AEs	X	X		X			
Treatment emergent serious AEs	X	X	X	X	X	X	X
Treatment emergent non-serious AEs	X	X					
TEAE with suspected drug relation to ribociclib	X	X					
TEAE leading to permanent discontinuation of study drug	X	X					
TEAE of special interest	X	x	x		X	X	X
Death (in pre-/on-/post-treatment period)	X		X				

The **incidence frequency table** presents the number, percentage and 95% confidence for occurrence of at least one event of the respective AE type. This table is separated by each of the observation period (pre-/on-/post-treatment) and total. Denominator (for each period) is the number of patients in the Safety Analysis Set (SAF).

The **two-level frequency table** calculates absolute and relative frequencies for MedDRA System Organ Classes (SOC) and Preferred Terms (PT) within SOCs. Again, the number of patients in SAF is used as denominator and each event is counted only once in the respective category. The MedDRA version currently available at time point of analysis is used for decoding.

The **frequency table for maximum severity** analyses the maximum CTC-AE grade and display n and % for each category (total, SOC, and PT). Again, the number of patients in SAF is used as denominator and each maximum severity is counted only once in the respective category.

All patient data are listed in CSR section 16.2. Additionally **data listings** relevant for safety assessment are presented in section 14.3.2. Here, the patient identification, the verbatim term given by the investigator, MedDRA preferred term and system organ class, start/end dates,

severity, seriousness, relationship to study drug and action taken are listed. The AE onset will also be shown relative (in number of days) to the date of initial dose.

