6.1 Study treatment

For this study, the term “investigational drug” refers to Novartis study drug ribociclib (LEE011). The other investigational drugs to be used in this study are letrozole as well as goserelin acetate for pre-and perimenopausal women; men may also be treated with goserelin acetate at the discretion of the investigator. Study treatment in this study refers to the combination of drugs and includes investigational drug (ribociclib) as well as letrozole and goserelin acetate.

Novartis will provide ribociclib and letrozole (and goserelin) for all patients who are enrolled prior to commercial availability of ribociclib. For patients enrolled afterwards within the approved indication according to SmPC, the investigator will prescribe both ribociclib and letrozole after evaluation of the individual medical patient need for the treatment with ribociclib and letrozole. Patients who are enrolled outside of the label according to SmPC will be provided with study drug by Novartis (i.e. patients in cohort B).

Patients enrolled after commercial availability of ribociclib and letrozole, who are to be treated within the label and are covered by private health insurance should contact their private health insurance to ensure that the insurance will cover the costs of the prescription.

Ribociclib will be supplied by Novartis or its designee as 200 mg film-coated tablets as individual patient supply packaged in bottles or blisters. Letrozole and goserelin acetate will be procured locally as it is commercially available in Germany. Storage conditions are described in the medication label.

All dosages prescribed and dispensed to the patient and all dose changes during the study must be recorded on the Dosage Administration Record eCRF. On the first day of each cycle, patients will receive an adequate drug supply (before commercial availability) or a prescription (after commercial availability) for self-administration at home.

The investigator must emphasize compliance and will instruct the patient to take ribociclib (LEE011) and letrozole as well as goserelin exactly as prescribed.

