8.1 Adverse events

8.1.1 Definitions and reporting

An adverse event is defined as the appearance of (or worsening of any pre-existing) undesirable sign(s), symptom(s), or medical condition(s) that occur after patient's signed informed consent has been obtained.

Abnormal laboratory values or test results occurring after informed consent constitute adverse events only if they induce clinical signs or symptoms, are considered clinically significant, require therapy (e.g., hematologic abnormality that requires transfusion or hematological stem cell support), or require changes in study medication(s).

Adverse events that begin or worsen after informed consent should be recorded in the Adverse Events CRF. Conditions that were already present at the time of informed consent should be recorded in the Medical History page of the patient's CRF. Adverse event monitoring should be continued for at least 30 days (or 5 half-lives, whichever is longer) following the last dose of study treatment. Adverse events (including lab abnormalities that constitute AEs) should be described using a diagnosis whenever possible, rather than individual underlying signs and symptoms. When a clear diagnosis cannot be identified, each sign or symptom should be reported as a separate Adverse Event.

Adverse events will be assessed according to the Common Terminology Criteria for Adverse Events (CTCAE) version 4.03. If CTCAE grading does not exist for an adverse event, the severity of mild, moderate, severe, and life-threatening, corresponding to Grades 1 - 4, will be used. CTCAE Grade 5 (death) will not be used in this study. If death is not caused by progression of the disease, it has to be reported as SAE on the SAE report form. Adverse events with death as outcome must be documented as SAE on the SAE report form.

The occurrence of adverse events should be sought by non-directive questioning of the patient (subject) during the screening process after signing informed consent and at each visit during the study. Adverse events also may be detected when they are volunteered by the patient (subject) during the screening process or between visits, or through physical examination, laboratory test, or other assessments.

As far as possible, each adverse event should be evaluated to determine:

- The severity grade (CTCAE Grade 1-4).
- Its duration (Start and end dates).
- Its relationship to the study drug (Yes or No).

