10.5.2.2 Adverse events (AEs)

Summary tables for adverse events (AEs) have to include only AEs that started or worsened during the on-treatment period, the **treatment-emergent** AEs. However, all safety data (including those from the pre and post-treatment periods) will be listed and those collected during the pre-treatment and post-treatment period are to be flagged.

The incidence of treatment-emergent adverse events (new or worsening from baseline) will be summarized by system organ class and or preferred term, severity (based on CTCAE grades), type of adverse event, relation to study treatment by pretreatment group.

Deaths reportable as SAEs and non-fatal serious adverse events will be listed by patient and tabulated by type of adverse event.

Data collected by AE CRFs will be coded using the MedDRA dictionary. The incidence of treatment-emergent adverse events (new or worsening from baseline) will be summarized by MedDRA system organ class and preferred term using frequency distributions. Additionally, AE will be summarized by maximum severity (based on CTCAE grades), and for AE with suspected drug relation, serious AE (SAE), and AE leading to permanent discontinuation of study drug. All information pertaining to AE noted during the study will be listed by patient, detailing the verbatim term given by the investigator, MedDRA preferred term and system organ class, start/end dates, severity, seriousness, relationship to study drug and action taken. The AE onset will also be shown relative (in number of days) to the date of initial dose.

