1.2 Study objectives and endpoints

Objectives and related endpoints are described in the table below (in accordance with Table 3-1 from the protocol).

Primary Objective	Endpoint

The primary objective of this study is the assessment of the clinical benefit rate after 24 weeks for the total population and for cohorts A and B separately:
 
1. Cohort A: postmenopausal women and men who received no prior treatment for advanced disease. (70% group)2. Cohort B: pre-, and perimenopausal women who received no prior treatment for advanced disease as well as pre-, peri- and postmenopausal women and men who received no more than 1 prior chemotherapy and 2 prior lines of endocrine therapy for advanced disease (30% group)	Clinical Benefit Rate (CBR) after 24 weeks of treatment as defined by RECIST 1.1 as percentage of patients with CR, PR or SD until week 24 or longer as well as patients with NCRNPD >24 weeks for patients with non-measurable disease

Secondary Objectives	Endpoint

To assess the clinical benefit rate (CBR) after 24 weeks among Cohort B1 and B2:
	
Clinical Benefit Rate (CBR) after 24 weeks of treatment as defined by RECIST 1.1 as percentage of patients with CR, PR or SD until week 24 or longer as well as patients with NCRNPD >24 weeks for patients with non-measurable disease

Progression-free survival (PFS) for the three different populations: Cohort A, Cohort B1, Cohort B2
	
PFS based on radiologic assessment by investigator using RECIST 1.1 criteria (e.g. median PFS, PFS rate at 12 and 18 months)

Overall survival (OS) for the three different populations, defined as the time from date of start of treatment to date of death due to any cause.
	
Overall survival (OS) (e.g. OS rate at 12 and 24 months)

Overall response rate (ORR) for the three different populations, defined as complete response or partial response as defined by RECIST 1.1
	
Overall Response Rate (ORR) after 24 weeks

To evaluate the safety and tolerability of ribociclib in combination with letrozole (and goserelin in premenopausal patients)
	
Frequency/severity of AEs AEs of special interest: Frequency, severity, frequency per patient, time to Event, duration of Event and recurrence

To evaluate patient reported outcomes for health related quality of life
	
Laboratory values Time to 10% deterioration in the global health status/QOL scale score of the EORTC QLQ-C30

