2.1.1 General definitions

Study treatment: The combination of drugs including investigational drug ribociclib as well as letrozole and goserelin acetate.

On-treatment period: Period the patient was exposed to any study treatment, i.e from the first administration of any study treatment at or after C1/D1 to the last administration of any study treatment (for ribociclib and letrozole documented on the Treatment Completion CRF and for Goserelin documented on the Dosage Administration record but not later than the End-of-study visit (see 5.2.1)

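### SAP 2.8.1 lists related adverse events for ribociclib only, while protocol 10.5.2.2 asks for relation to the whole study treatment; the narrowing is not declared

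*SAP*

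**What the plan says.** The safety objective concerns the combination: "To evaluate the safety and tolerability of ribociclib in combination with letrozole (and goserelin in premenopausal patients" (SAP 1.2, as in protocol Table 3-1).

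Protocol 10.5.2.2 names the factors by which TEAE incidence is summarised, among them "type of adverse event, relation to study treatment by pretreatment group". Later in the same section a second list asks for further summaries "for AE with suspected drug relation, serious AE (SAE), and AE leading to permanent discontinuation of study drug", without naming a drug.

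Study treatment is defined alike in both documents. Protocol 6.1: "Study treatment in this study refers to the combination of drugs and includes investigational drug (ribociclib) as well as letrozole and goserelin acetate". SAP 2.1.1: "The combination of drugs including investigational drug ribociclib as well as letrozole and goserelin acetate".

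The table plan in SAP 2.8.1 has one row on causality, "TEAE with suspected drug relation to ribociclib", with an incidence table and a table by system organ class and preferred term (SOC/PT). Otherwise, causality appears in SAP 2.8.1 only as a column of the patient listings. SAP section 4, on changes to protocol-specified analyses, mentions only time to response and duration of response.

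On data capture, protocol 8.1.1 lists for each adverse event "Its relationship to the study drug (Yes or No". Protocol 8.2.2 requires causality for each specific study treatment, but only for serious adverse events and on the serious adverse event report form.

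**The concern.** The protocol's summary and the SAP's row count different things. An event that the investigator attributes to letrozole or goserelin, but not to ribociclib, is related under the protocol's definition and not related under the SAP's row. The protocol itself describes such events: section 1.2.2 lists hot flashes, arthralgia and myalgia for letrozole, and section 1.2.3 lists hot flushes, headache, sweating and others for goserelin.

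At stake is whether the related-event rates describe the regimen named in the safety objective or one component of it. A reader who sets them beside protocol Table 1-5, which reports suspected relationship to study treatment in the pivotal trial, would be comparing two definitions without being told so. Because section 4 is silent, nothing shows whether the narrowing was intended.

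**Working it through.** **Step 1: the texts side by side.**

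| Item | Protocol | SAP |
|---|---|---|
| Study treatment | Ribociclib, letrozole, goserelin (6.1) | The same (2.1.1) |
| Causality basis for TEAE tables | Study treatment (10.5.2.2, first list); an unnamed drug (second list) | Ribociclib (2.8.1) |
| Declared as a change | n/a | No (section 4) |

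The mismatch follows from the wording alone and needs no arithmetic.

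**Step 2: what it does to the counts.** This depends on the adverse event form, which the documents do not show. There are three possibilities.

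1. Causality was recorded for each component. Events attributed solely to letrozole or goserelin then leave the related-event rates, and the protocol's table is missing from SAP 2.8.1.
2. There was one item covering the combination. No event is lost, but the ribociclib label on the table is wrong.
3. There was one item about ribociclib only. The SAP label is right, but the protocol's summary cannot be produced for non-serious events, and section 4 should say so.

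The SAP needs a correction in each case. Only the first changes a rate.

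**Step 3: size in the first case.** The plan gives no figure to reproduce. As an illustration, take rates related to study treatment from the ribociclib arm of protocol Table 1-5:

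- hot flush: 51/334 = 15.3% (placebo plus letrozole: 63/330 = 19.1%)
- arthralgia: 48/334 = 14.4% (placebo plus letrozole: 52/330 = 15.8%)

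These two are no more frequent with ribociclib than without it, so attribution to letrozole alone is plausible for some patients. Let s be the share of affected patients whose event is attributed solely to letrozole or goserelin. The documents do not give s, so it is varied over its whole range:

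ribociclib-related rate = study-treatment-related rate × (1 − s)

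| s (assumed) | Hot flush | Arthralgia |
|---|---|---|
| 0 | 15.3% | 14.4% |
| 0.25 | 11.5% | 10.8% |
| 0.50 | 7.6% | 7.2% |
| 0.75 | 3.8% | 3.6% |
| 1 | 0% | 0% |

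For scale, at the planned 500 patients these rates correspond to 500 × 51/334 ≈ 76 patients with related hot flush and 500 × 48/334 ≈ 72 with related arthralgia before any reduction.

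**The case against.** The strongest reply is that the SAP may simply name what was collected. Protocol 8.1.1 shows one yes/no item, and the protocol often uses study drug for ribociclib alone: section 6.6 defines study drug discontinuation as withdrawal from ribociclib. The SAP rows also follow the protocol's second list, which speaks of drug relation without saying which drug. This stands as a reason not to assert a loss. It does not settle the wording. Section 6.6 also uses study drug to cover letrozole, section 8.1.1 later asks that the suspected relationship to study treatment be reassessed at each visit, and the first list in 10.5.2.2 is explicit.

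It is also fair that hot flush and arthralgia remain fully visible. All TEAEs are tabulated regardless of causality, by incidence, SOC/PT and maximum severity. Serious events and discontinuations have their own tables. The SAP further relies on a RAP module 7.1 that is not among the documents, so the supportable statement is that SAP 2.8.1 lists no any-component table, not that none exists anywhere.

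A reader might infer more from Table 1-5 than it bears:

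- **A fall of about 15 points for hot flush.** That is the ceiling at s = 1, and the floor is zero.
- **The 75.5% of placebo-plus-letrozole patients with a suspected event as a measure of what is lost.** It is not one. In the ribociclib arm, 59.6% had suspected neutropenia (3.9% on placebo) and 43.1% suspected nausea (16.4%). Many patients with a letrozole-attributed event would therefore still count through another event.
- **The largest loss in cohort B.** No figure supports this. Cohort B2 includes postmenopausal women, who are not scheduled for goserelin, and cohort A includes men, who may receive it.

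**Conclusion.** The inconsistency is established: the protocol specifies relation to the combination, the SAP's single causality row is limited to ribociclib, and the change is undeclared. It bears on a stated secondary objective and should be corrected.

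Its numerical effect is not established. A loss from the related-event rates requires that causality was recorded by component and that some events were attributed solely to letrozole or goserelin. The documents show component-level causality only for serious events and give no attribution split. A reader might conclude that the regimen will be reported as better tolerated than it was. The documents do not support that, because the loss may be zero, events attributed to both ribociclib and a partner drug stay in, and the tables regardless of causality are untouched.

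**What to change.** In SAP 2.8.1, add a row *TEAE with suspected relation to study treatment (any component)* as the protocol-specified table, with the same incidence and SOC/PT outputs, and keep the ribociclib row as an additional table.

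Before that, check the causality item on the adverse event form. If it was a single item:

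- label the table by what the item asked;
- present a related serious adverse event table from the per-component attribution that protocol 8.2.2 requires, after confirming that this field, held on the report form, is available for analysis;
- declare any remaining departure from protocol 10.5.2.2 in SAP section 4.

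The cost is one extra incidence and SOC/PT table pair and a few lines of SAP wording. No new data collection is needed.
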